8.6. Study Exit Criteria and Procedures

All patients that sign an informed consent document for this study will have the study exit reason documented in the medical record and on the appropriate eCRF. Patients may exit the study for any of the following reasons:

- **Screen Failure:** Patients who are consented to participate in the study, but do not fulfill enrollment criteria.

- **Study Device Attempted but Not Implanted:** Enrolled patient for whom the implant procedure was prematurely aborted will be followed either for 30 days (for only safety evaluations) OR until resolution, stabilization, or is adequate explanation of any implant-related AEs and then exited from the study. Examples include:
 - Procedure attempted (i.e. skin incision to introduce the EVOQUE System) but patient did not receive a study device
- **Study Device Re-intervention/Explant:** Patient who has a surgical re-intervention for study device explant will be followed for 30 days after the re-intervention for safety evaluations only or until resolution of any AEs related to the re-intervention and then exited from the study. Note: a patient who has a percutaneous re-intervention where the study device remains in place will continue to be followed for the duration of the study.
- **Withdrawal**
 - **Patient Withdrawal:** A patient may voluntarily withdraw from the clinical study at any time, without penalty or loss of benefits to which they are otherwise entitled.
 - **Physician Withdrawal:** An Investigator also has the right to withdraw a patient if s/he feels it is in the best interest of the patient to do so.
- **Patient death**
- **Lost to Follow-up**
 - If a patient cannot be reached for a follow-up visit, the Investigator will document contact efforts and/or efforts to obtain hospital records in the appropriate eCRF. If a patient cannot be reached in any way, or misses a visit, the patient will be considered “unable to contact” for that time interval.
 - After 3 documented unsuccessful attempts to make contact, a certified letter will be sent to the patient’s residence. If there is no response after a certified letter is sent, the patient will be classified as “lost to follow-up”.
- **Completion Per Protocol**

Withdrawn patients will not have any study follow-up visits or procedures after the time of study exit. All data collected up until the time of withdrawal, including imaging studies such as echocardiography scans, will be analyzed.

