*For patients who experience a stroke during the study, mRS will be conducted closest to 90 days post event. It is recognized that an assessment of stroke is incomplete without an appropriate measurement of the disability resulting from the stroke, hence, mRS closest to 90 days post event will be used to assess clinical disability. Every effort should be made to have a neurologist or neurology fellow perform the neurological assessments, or alternatively, a trained research team member certified in stroke assessment. mRS can be obtained by a certified research team member via phone interview with the patient or caregiver member if the patient is unable to visit the research office.^{53,54}

** Should be collected at the 30 day and 12 month follow-up visits according to the current version of the acquisition guide unless medically contraindicated or patient refuses.

†Blood samples will be analyzed by local institution and any remaining blood sample will be discarded according to institutions regulations.

Table 13: Follow-up Visit Windows

Scheduled Follow-up Interval	Follow-Up Window
Discharge or Day 7 (whichever comes first)	± 0 days
1 month (30 days)	± 7 days
6 months (180 days)	-90/+30 days (90 to 210 days)
Annually (365 days) up to 5 years	± 45 days

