12.2. Analysis Populations

Analysis will be performed for the Enrolled, As-Treated (AT), Per-Protocol (PP) populations defined below:

- **Enrolled Population:** all patients enrolled in the study, defined as patients who sign informed consent and have had the study procedure attempted (attempted defined as skin incision for study device). Enrolled population will be used for the safety analyses.
- **As-Treated Population:** is a subset of the enrolled population who have had the study device implanted at the exit of procedure room. The AT population will be the analysis population for performance and functional endpoint analysis.
- **Per-Protocol Population:** is a subset of the AT population who had no protocol deviations relating to inclusion and exclusion criteria for the trial.

Additional analyses of performance and safety data using the PP population will be performed if there is/are a clinically meaningful difference(s) from the enrolled and the as-treated populations.

The safety analysis will be performed for enrolled population with due consideration given to the respective required follow-up intervals and the performance analysis including device success, procedural success and clinical success will be performed for implanted population.

The echocardiographic and functional analyses will be a summarization of measures of hemodynamic performance including reduction of tricuspid regurgitation, NYHA Functional Class, 6-minute walk test, and Quality of Life based on the implanted population. Patients that undergo any type of repair or replacement procedure for the tricuspid valve will be excluded from the echocardiographic analysis at the time of the reintervention and summarized in a table.

Clinical endpoints including all-cause mortality, heart failure hospitalizations, and non-elective re-intervention related to the device will be analyzed based on implanted population.

For patients participating in the sub-study, a separate data analysis plan will be developed to analyze the actigraphy data collected from the activity monitor and electronic patient reported outcome data collected from the eDiary.

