12.3. General Approach

For continuous variables, results will be summarized with the number of observations, mean, standard deviation, median, minimum, maximum, and 90% confidence interval (CI) by normal approximation. For categorical variables, results will be summarized with patient count, percentage, and 90% CI by normal approximation, where appropriate.

Survival analysis techniques will be used to analyze time-to-event variables. Patients without events will be censored at their participation date in the study. For patients who did not have an event but remain in the study, they will be censored at the database extract date. Time to first event curves will be constructed using Kaplan-Meier estimates.

Descriptive statistics will be presented at each assessment, including change from baseline to subsequent time point for selected endpoints. For the determination of event rates, the number of all patients in the patient population will be used as the denominator. For variables ascertained at follow-up visit, the denominator will be based on number of evaluable patients. Unless otherwise noted, patients with missing data will be excluded from the denominator.

When the sample size is small (e.g., <10 patients), analysis may be performed in the form of listings only.

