### 6. DATA AND ANALYSIS CONVENTIONS

#### 6.1 General Conventions

For continuous variables, results will be summarized with the number of observations, mean, standard deviation, median, minimum, maximum, and 90% confidence interval (CI) by normal approximation. For categorical variables, results will be summarized with patient count, percentage, and 90% CI by normal approximation, where appropriate.

Survival analysis techniques will be used to analyze time-to-event variables. Patients without events will be censored at their last participation date in the study. For patients who did not have an event but remain in the study, they will be censored at the database extract date. Time to first event curves will be constructed using Kaplan-Meier estimates. Descriptive statistics will be presented at each assessment, including change from baseline to subsequent time point for selected endpoints. For the determination of event rates, the number of patients in the patient population who have had the events or have been followed up to the upper bound of the follow-up visit window will be used as the denominator. Unless otherwise noted, patients with missing data will be excluded from the denominator.

When the sample size is small (e.g., <10 patients), analysis may be performed in the form of listings only.

Quality of life questionnaires will be scored according to algorithms provided by the vendor. The various summary scores produced by the algorithms will be analyzed as continuous variables.

Unless otherwise specified, confidence limits will be two sided, using alpha = 0.05.

Unless otherwise specified, the precise form of each algorithm will be the default of SAS, using the latest release installed at Edwards Lifesciences (Edwards) at the time of analysis.

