### 8.1 Safety Endpoint

The safety endpoint of MAEs at 30 days shall be analyzed via the Kaplan-Meier method for the Enrolled and AT populations. In addition, the event rates of individual component of MAEs will also be calculated at 30 days, 6 months, and annually until 5 years post-procedure by the Kaplan-Meier method:

- Cardiovascular mortality •
- Myocardial infarction (MI) •
- Stroke •
- Renal complications requiring unplanned dialysis or renal replacement therapy •
- Severe bleeding (includes fatal, life-threatening, extensive, or major bleeding, as defined by MVARC) •
- Non-elective tricuspid valve re-intervention, percutaneous or surgical •
- Major access site and vascular complications •
- Major cardiac structural complications •
- Device-related pulmonary embolism

The number and percentage of patients with at least one MAE at 30 days will be summarized. The number of MAE at 30 days, 6 months, and annually will be reported as well. Additional analyses of safety endpoints using the PP population will be performed if there is/are a clinically meaningful difference(s) from the enrolled and AT populations.

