#### 8.2 Performance Endpoints

Device success, procedural success, and clinical success will be summarized by counts and percentages. For device success, the percentage will be based on the number of attempted device (per device analysis) in the Enrolled population. Procedural success will be analyzed based on the number of patients (per patient analysis) in the AT population, and device success per patient will be defined as at least one device success. Clinical success will be analyzed based on the number of patients (per patient analysis) in the AT population.

Additional analyses of performance endpoints using the PP population will be performed if there is/are a clinically meaningful difference(s) from the enrolled and AT populations.

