## 10. CHANGES FROM PROTOCOL SPECIFIED ANALYSES

The patient-centered exploratory endpoints are not specified in the study protocol and only described in Section 3.7 of this SAP.

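### SAP 6.1 drops event-free patients who leave on days 30 to 36 from the crude 30-day event percentage: a small upward departure from Protocol 12.3 that SAP Section 10 does not list

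*SAP*

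**What the plan says.** Protocol 12.3 states for event rates that "the number of all patients in the patient population will be used as the denominator". A separate sentence there reserves an evaluable-patient denominator for variables measured at a visit. A further sentence removes patients with missing data unless otherwise noted, and Protocol 12.8 limits analyses to patients with the data they require.

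SAP 6.1 keeps the missing-data sentence but replaces the event-rate denominator by those patients in the population "who have had the events or have been followed up to the upper bound of the follow-up visit window". Protocol Table 13 sets the 30-day visit at ± 7 days.

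SAP 8.1 analyses the 30-day MAE endpoint by Kaplan-Meier in the Enrolled and As-Treated (AT) populations, and adds a crude summary: "The number and percentage of patients with at least one MAE at 30 days will be summarized".

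The Enrolled population (SAP Section 4) includes patients in whom the procedure was attempted but no device was implanted. Under Protocol 8.6 such a patient "will be followed either for 30 days (for only safety evaluations) OR until resolution" or stabilisation of implant-related events, and then exits.

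SAP Section 10 declares one change only: "The patient-centered exploratory endpoints are not specified in the study protocol and only described in Section 3.7 of this SAP".

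**The concern.** Entry to the SAP denominator depends on the outcome. A patient with the event is always in. A patient without it must also be followed to day 37, a week past the time point being estimated. Someone known to be free of MAE through day 30 who then exits as the Protocol allows has nothing missing for a 30-day endpoint, yet leaves the denominator. The same patient with an MAE would stay.

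At stake is the crude percentage printed beside the Kaplan-Meier estimate for the study's safety endpoint, in a single-arm study that is meant to guide later designs. The rule can only raise that percentage relative to the all-patient one, and a reader of SAP Section 10 would not learn that the denominator had changed.

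**Working it through.** The documents give no expected MAE rate, exit rate or precision target, and SAP 2.3 says N has no statistical justification. There is therefore no planned figure to reproduce.

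**Inputs from the documents.** N up to 200 (SAP 2.3). Visit window 30 ± 7 days (Protocol Table 13). 90% CI by normal approximation (SAP 6.1).

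**Assumptions, not in the documents.** True 30-day MAE rate 20%, varied from 10% to 30%. Between 4 and 12 Enrolled patients not implanted, a quarter of them with an MAE, which leaves 3 to 9 event-free. All of these exit on days 30 to 36.

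**Step 1, the bound.** 30 + 7 = day 37.

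**Step 2, who counts at 30 days.**

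| Patient | Protocol 12.3 | SAP 6.1 |
|---|---|---|
| MAE by day 30 | in | in |
| Event-free, followed to day 37 or later | in | in |
| Event-free, exits on days 30-36 | in | out |
| Event-free, exits before day 30 | arguably out (missing data) | out |

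Only the third row is a clear difference.

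**Step 3, direction.** Let E be the number of patients with an MAE by day 30 and x the number in the third row. The crude figure moves from E/N to E/(N − x), which is never smaller.

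**Step 4, size in the Enrolled population.** E = 0.20 × 200 = 40.
- x = 3: 40/197 = 20.3%
- x = 9: 40/191 = 20.9%
- If half of these patients are followed past day 37: 40/198.5 = 20.2% and 40/195.5 = 20.5%
- With x still 3 to 9 and a 10% rate: 20/197 = 10.2% and 20/191 = 10.5%
- With x still 3 to 9 and a 30% rate: 60/197 = 30.5% and 60/191 = 31.4%

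Each further event-free exit on days 30 to 36 adds about 0.1 point at 20% (40/199 = 20.1%). In the AT population, which contains no non-implanted patients, only such other exits matter.

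**Step 5, scale.** 90% half-width at 20%: 1.645 × √(0.2 × 0.8/200) = 0.0465, or about 4.7 points.

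**Step 6, check by simulation.** One million patients, true risk 20%, MAEs mostly early, exit independent of events.

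| Exits before day 30; days 30-36 | All patients | Event or followed to day 30 | SAP 6.1 (day 37) | Kaplan-Meier |
|---|---|---|---|---|
| 2%; 3% | 19.9% | 20.2% | 20.7% | 19.9% |
| 5%; 5% | 19.8% | 20.7% | 21.6% | 20.0% |

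Moving the bound from day 30 to day 37 accounts for 0.5 and 0.9 points respectively. The rest of the excess comes from dropping exits before day 30.

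**The case against.** The strongest reply is that the Protocol does not stop at all patients. Its missing-data sentence (12.3) and available-data rule (12.8) can be read to exclude an event-free patient who leaves on day 10, since the 30-day outcome is unknown, while keeping a patient with an MAE on day 5. On that reading the Protocol's own denominator already depends on the outcome before day 30. This stands. A reader might count every event-free exit before day 37 as a departure and so obtain a larger figure, but the documents support that clearly only for days 30 to 36.

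It might also be said that Protocol 12.2 permits the rule, because the safety analysis is to be done "with due consideration given to the respective required follow-up intervals". This does not stand. The required interval for a 30-day endpoint is 30 days, and Protocol 8.6 sets 30 days as one of the two follow-up routes for non-implanted patients. Nothing there requires day 37.

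Third, SAP 8.1 does not expressly invoke the 6.1 denominator for its crude percentage, and SAP 6.1 does not define what counts as followed. Applying 6.1 there is the natural reading, since 8.1 gives no other denominator, but it remains a reading.

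A reader might infer that the rule alone explains any gap between the crude figure and Kaplan-Meier. It does not: with censoring, an all-patient percentage also differs from Kaplan-Meier (19.8% against 20.0% in the second simulated case). Nor is there a firm conflict with SAP 8.2, where "Clinical success will be analyzed based on the number of patients (per patient analysis) in the AT population". That sentence sets the unit of analysis, in contrast to the per-device analysis, and Clinical success also needs a discharge echocardiogram, so its evaluable set may differ anyway. A larger distortion at a data cut during enrolment is conceivable, but the plan specifies no such cut.

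**Conclusion.** The departure is real and minor. SAP 6.1 removes event-free patients with complete 30-day outcomes who exit on days 30 to 36, conflicts with Protocol 12.3, and is absent from SAP Section 10. If 6.1 governs the crude percentage in SAP 8.1, that percentage is raised relative to the all-patient one. On the assumptions above, the rise in the Enrolled population is 0.3 to 0.9 points at a 20% rate, and less if some non-implanted patients are followed longer. The number of such patients and the MAE rate are both assumed.

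A reader might conclude that the study's safety result is biased. The documents do not support that: the specified 30-day MAE analysis is Kaplan-Meier, which does not use this denominator, and no hypothesis test, success threshold or sample-size calculation depends on the crude figure.

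**What to change.** In SAP 6.1, remove the window-upper-bound condition for 30-day event percentages. Use all patients in the analysis population as the denominator and count events to day 30.

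Report the number who left event-free before day 30, and state openly that for this output the missing-data sentence in Protocol 12.3 and SAP 6.1 does not remove them. The drawback is small: these patients count as event-free, so the percentage can run slightly low. For that reason keep the Kaplan-Meier estimate as the main 30-day MAE figure.

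List any remaining departure from Protocol 12.3, including the override of its missing-data sentence, in SAP Section 10.

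The cost is SAP wording and a small programming change, with no new data.

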#### 6.2 Handling of Missing Data

For AEs with partial onset dates, if the year is not missing, imputation will be performed by finding the earliest possible date on or after the index procedure. If the year is missing, no imputation will be performed.

E	Revision Date: August 1, 2022		Rev		For Use Only by Affiliates of Edwards Lifesciences	Page 13 of 18
Edwards	Title	Statistical Analysis P	lan foi	r TRIS	CEND Study	v (2019-06)

For endpoint-related AEs (such as MAEs) with partial dates, in addition to applying the imputation method above, the sponsor will review the events and related records on a case-by-case basis, and manually verify the imputed dates. All imputations will be documented and filed in the Trial Master File (TMF).

For missing data due to patient withdrawal or lost to follow-up in the analyses of time-dependent endpoints, the patients will be censored on the last participation date as stated above.

Unless otherwise specified, all statistical analyses will be performed using only those patients with available data required for endpoint analysis, and no other missing value imputation will be performed.

## 7. SUMMARY OF BASELINE INFORMATION

### 7.1 Patient Enrollment and Accountability

The number of enrolled patients will be summarized overall and by investigational site. The table will be sorted by enrollment going from the highest enrollment site to the lowest enrollment site. The number of enrolled patients in each analysis population will be summarized as well.

The summary of subject disposition will include numbers of enrolled patients, eligible for visit, and non-eligible for visit by follow-up visit.

## 7.2 Demographics and Baseline Characteristics

Descriptive summary statistics of demographics and baseline characteristics will be presented for all three analysis populations. All demographics and baseline data will be listed as well.

- Age (years)
- Gender
- Body Mass Index (BMI)
- STS Mortality Score for MV Replacement Only (%)
- EuroSCORE II (%)
- TR grade (assessed by TTE)
- NYHA classification
- Clinical Frailty
- Katz ADL

## 7.3 Medical History and Prior Intervention

Medical history and prior interventions grouped by event types (cardiovascular, cardiovascular intervention and surgeries, and non-cardiovascular) will be summarized by counts and percentages for all three analysis populations.

#### 7.4 **Procedural Information**

Procedural information will be summarized including but not limited to procedure duration and total length of stay for the index hospitalization for all three analysis populations.

#### 8. STATISTICAL ANALYSIS OF STUDY ENDPOINTS

For statistical analyses of the study endpoints, Enrolled and AT populations will be used, unless otherwise stated.

### 8.1 Safety Endpoint

The safety endpoint of MAEs at 30 days shall be analyzed via the Kaplan-Meier method for the Enrolled and AT populations. In addition, the event rates of individual component of MAEs will also be calculated at 30 days, 6 months, and annually until 5 years post-procedure by the Kaplan-Meier method:

- Cardiovascular mortality •
- Myocardial infarction (MI) •
- Stroke •
- Renal complications requiring unplanned dialysis or renal replacement therapy •
- Severe bleeding (includes fatal, life-threatening, extensive, or major bleeding, as defined by MVARC) •
- Non-elective tricuspid valve re-intervention, percutaneous or surgical •
- Major access site and vascular complications •
- Major cardiac structural complications •
- Device-related pulmonary embolism

The number and percentage of patients with at least one MAE at 30 days will be summarized. The number of MAE at 30 days, 6 months, and annually will be reported as well. Additional analyses of safety endpoints using the PP population will be performed if there is/are a clinically meaningful difference(s) from the enrolled and AT populations.

#### 8.2 Performance Endpoints

Device success, procedural success, and clinical success will be summarized by counts and percentages. For device success, the percentage will be based on the number of attempted device (per device analysis) in the Enrolled population. Procedural success will be analyzed based on the number of patients (per patient analysis) in the AT population, and device success per patient will be defined as at least one device success. Clinical success will be analyzed based on the number of patients (per patient analysis) in the AT population.

Additional analyses of performance endpoints using the PP population will be performed if there is/are a clinically meaningful difference(s) from the enrolled and AT populations.

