#### 3.2 **Performance Endpoints**

#### **Device Success**

• Device success is achieved if the study device is deployed as intended and the delivery system is successfully retrieved as intended at the time of the patient's exit from the OR/cardiac catheterization laboratory. This endpoint will have a per device analysis performed.

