#### Procedural Success

• Procedural success is "device success" without clinically significant paravalvular leak (PVL) on a transthoracic echocardiogram (TTE, assessed by the echo core lab) at time of discharge. This endpoint will have a per patient analysis performed.

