#### Clinical Success

• Clinical success is "procedural success" without any MAEs at 30 days. This endpoint will have a per patient analysis performed.

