#### **ANALYSIS POPULATIONS** 4.

Analysis will be performed for the Enrolled, As-Treated (AT), and Per-Protocol (PP) populations defined below:

- Enrolled Population: All patients enrolled in the study, defined as patients who sign informed consent and have had the study procedure attempted (attempted defined as skin incision for study device). Enrolled population will be used for the safety analyses.
- As-Treated Population: A subset of the enrolled population who have had the study device implanted at • the exit of procedure room. The AT population will be the analysis population for performance and functional endpoint analysis.
- Per-Protocol Population: A subset of the AT population who had no protocol deviations relating to • inclusion and exclusion criteria for the trial.

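### Procedural and clinical success are computed only in implanted patients, so enrolled patients who leave without a device, who fail both endpoints by definition, drop out of the denominator

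*SAP*

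**What the plan says.** SAP 3.2 builds the three performance endpoints in a chain. At the base, "Device success is achieved if the study device is deployed as intended and the delivery system is successfully retrieved as intended", judged when the patient leaves the room. Procedural success is device success plus absence of clinically significant paravalvular leak on the discharge echocardiogram. The last link is "Clinical success is 'procedural success' without any MAEs at 30 days".

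SAP 8.2 then assigns populations:

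- Device success: "For device success, the percentage will be based on the number of attempted device (per device analysis) in the Enrolled population".
- Procedural success: "Procedural success will be analyzed based on the number of patients (per patient analysis) in the AT population", with the supporting rule that "device success per patient will be defined as at least one device success".
- Clinical success: "Clinical success will be analyzed based on the number of patients (per patient analysis) in the AT population".

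SAP section 4 gives the general rule: "The AT population will be the analysis population for performance and functional endpoint analysis". Under Protocol 12.2 and SAP section 4, a patient is Enrolled after consent and skin incision for the study device. AT is the subset who leave the procedure room with the device implanted. Protocol 12.2 and 12.6 place all three success endpoints on the implanted population.

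**The concern.** A patient has to pass the first step of the endpoint to be counted at all. Protocol 8.6 has an exit category for patients in whom the device was attempted but not implanted. Such a patient cannot have device success, and so can have neither procedural nor clinical success. With AT as the denominator, that failure disappears instead of being counted.

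The study is meant to evaluate the performance of the system and to guide the design of later studies (Protocol section 4, SAP 2.1). A later trial would treat patients in whom implantation is attempted, since nobody knows at incision who will end up implanted. An AT rate carried forward as the expected success rate for those patients would be too high whenever at least one implant attempt fails. The error can go in one direction only.

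**Working it through.** **1. Does anything else in the plan restore these patients?**

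- The opening of SAP section 8 uses both Enrolled and AT by default, but gives way where another population is named. SAP 8.2 names one.
- The conditional Per-Protocol analysis cannot help, because Per-Protocol is a subset of AT. SAP 8.2 triggers it by a difference from the Enrolled and AT results, yet plans no Enrolled result for these two endpoints.
- Device success is on Enrolled but counted per device. The per-patient version serves only as an input to procedural success, which is on AT.
- The exploratory success endpoints in SAP 3.7 and 8.7, including technical success, are also on AT.
- SAP 7.1 tabulates population sizes, not success rates.
- A major adverse event in a non-implanted patient counts in the Enrolled safety analysis (SAP 8.1) but cannot count against clinical success.

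No planned output restores them.

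**2. Size of the gap.** There is no figure in the plan to reproduce: the documents state no expected success rate and no non-implant rate, and SAP 2.3 says the sample size has no statistical justification. The only input from the documents is N = 200, the planned maximum. The values of f and of the AT rate below are assumptions.

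Let x be the number of successes. Non-implanted patients contribute none, so x is the same in both populations:

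- AT rate = x/(N − f); Enrolled rate = x/N
- Gap = x/(N − f) − x/N = AT rate × f/N

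Gap in percentage points, N = 200:

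| AT rate | f = 0 (0%) | f = 2 (1%) | f = 6 (3%) | f = 10 (5%) | f = 20 (10%) |
|---|---|---|---|---|---|
| 95% | 0 | 0.95 | 2.85 | 4.75 | 9.5 |
| 90% | 0 | 0.9 | 2.7 | 4.5 | 9.0 |
| 80% | 0 | 0.8 | 2.4 | 4.0 | 8.0 |
| 70% | 0 | 0.7 | 2.1 | 3.5 | 7.0 |

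**3. Comparison with sampling error.** SAP 6.1 gives 90% normal-approximation intervals for categorical variables, so the half-width is 1.645 × √(p(1 − p)/n).

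- AT rate 90%: 3.49 points at n = 200. At f = 8, n = 192, the half-width is 3.56 and the gap is 0.90 × 8/200 = 3.60. The gap overtakes at about 4% non-implants.
- AT rate 80%: 4.65 points at n = 200. At f = 12, n = 188, both are 4.80 to two decimals. The crossing is at about 6%.

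These crossing points are approximate, because 90% of 192 and 80% of 188 are not whole patients.

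**4. Example in whole patients, f = 10.**

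- AT: 171/190 = 90.0% (90% CI 86.4 to 93.6)
- Enrolled: 171/200 = 85.5% (90% CI 81.4 to 89.6)

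The Enrolled estimate lies below the lower limit of the AT interval.

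The formula assumes that success status is known for every implanted patient. SAP 6.1 and 6.2 drop patients with missing data, so missing discharge echocardiograms would change both denominators.

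**The case against.** The choice is declared, and for these two endpoints it follows the protocol. An AT rate answers a legitimate question, success among implanted patients, and is labelled as such. Failed attempts are not hidden: device success covers all attempted devices, and major adverse events and other adverse events are reported on Enrolled. A reader can subtract the population sizes in SAP 7.1 to find f, and can divide the AT success count by the Enrolled N. The gap may be zero. At 1 to 3% non-implants it is smaller than the 90% half-width when the AT rate is 90% or 80%, and nothing in the documents supports the higher non-implant rates. The study is descriptive, so the omission might be seen as a reporting preference.

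Most of these facts stand, and they limit the consequence. They do not remove the problem. Agreement between the documents does not turn a rate conditional on implantation into a rate for attempted patients, and the objective concerns the system, not only completed implants. The SAP has itself already moved device success from the implanted population to Enrolled, leaving the two endpoints built on it behind. That a reader could calculate the missing rate shows how cheaply it could be reported.

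**Conclusion.** The concern holds. Under the plan's own definitions, an enrolled patient without a device at room exit fails procedural and clinical success and is absent from both rates, with no planned analysis that puts the patient back. The planned rates equal the Enrolled rates if everyone is implanted and exceed them otherwise, by the AT rate times f/N. Across the assumed range of 1 to 10% non-implants and AT rates of 70 to 95%, that is 0.7 to 9.5 points. All of these inputs except N = 200 are assumptions.

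No error rate, power calculation or decision rule is involved. What is affected is how two of the three performance endpoints are read and reused. This should be fixed before the results are reported.

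**What to change.** - **SAP 8.2:** report procedural and clinical success per patient in the Enrolled population, counting every patient without an implanted device at room exit as a failure, and keep the AT rates as supportive. This rule also settles a device deployed and then removed before exit.
- **Missing data:** state that a non-implanted patient is a failure and not a missing observation. Otherwise the available-data rule in SAP 6.2 could remove the same patients again for want of a discharge echocardiogram.
- **SAP section 4:** adjust the sentence that makes AT the population for performance.
- **SAP section 10:** list the change as a departure from Protocol 12.2 and 12.6. Add the existing move of device success to Enrolled, a separate documentation gap: section 10 currently lists only the exploratory endpoints.

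The cost is SAP wording, one extra table column and the section 10 entry. Implant status is known at room exit, so no new data are needed. The headline rates may be somewhat less favourable.
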